10.5.2 Solicited AEs

Solicited local AEs (injection site pain, redness, swelling and itching) and solicited systemic AEs (chills, fever, nausea/vomiting, diarrhea, headache, fatigue, myalgia and arthralgia) information is collected for Phase 2b subjects for each day of CVnCoV/placebo vaccination (i.e. dose 1 and dose 2) and for the following 7 days after each CVnCoV/placebo dose. Subjects record any occurrence of an AE, grading of severity, and medication for treatment of the AE in an eDiary.

Subjects' eDiaries are reviewed by the investigator and available information on solicited local and systemic AEs with a grade > 0 is integrated into the CRF, including assessment of severity on an intensity scale of mild, moderate, and severe (Grade 1 – Grade 3), see Table 6 and Table 7. Note that events with a severity Grade 0 are not recorded as AEs in the CRF.

Additional solicited AEs may be recorded by the investigator based on CRF review if the recording within the diary is deemed incomplete.

In case there is more than one solicited AE with the same relationship to study treatment on a specific day with the same type of reaction (e.g. myalgia, injection site pain, nausea/vomiting) but recorded as different events, records are collapsed for that specific diary day. Thereby, if there are overlapping events with the same relationship on a given diary day, they are collapsed and reported with the highest severity grade on that day. Overlapping events with different relationship to study treatment are not collapsed.

Solicited events reported as "Nausea" and "Vomiting" are considered to be of the same reaction type "Nausea/Vomiting".

Table 6: Intensity Grading* for Solicited Local Adverse Events

AE	GRADE	DEFINITION
PAIN AT INJECTION SITE	0	Absent
	1	Does not interfere with activity
	2	Interferes with activity and/or repeated use of non-narcotic pain reliever >24 hours
	3	Prevents daily activity and/or repeated use of narcotic pain reliever
REDNESS	0	<2.5 cm
	1	2.5 – 5 cm
	2	5.1 – 10 cm
	3	>10 cm
SWELLING	0	<2.5 cm
	1	2.5 – 5 cm and does not interfere with activity
	2	5.1 – 10 cm or interferes with activity
	3	>10 cm or prevents daily activity
ITCHING	0	Absent
	1	Mild, no interference with normal activity
	2	Moderate, some interference with normal activity
	3	Significant, prevents normal activity

* FDA TOXICITY GRADING SCALE

Solicited AEs are assigned to first or second CVnCoV/placebo dose based on the (reported or imputed) AE date. Solicited AEs occurring before dose 2 are assigned to dose 1. Solicited AEs occurring on or after dose 2, are assigned to dose 2.

Solicited local AEs are always considered related to trial vaccine. Relationship to trial vaccine for solicited systemic AEs is assessed by the investigator and recorded on the CRF.

If not stated otherwise, data as recorded on the CRF is used for analysis of solicited AEs. However, subject's diary data is used to assess their eligibility for the SASsol (see Section 9.6.1) as follows:

- If at least one question on occurrence of a local or systemic AE is answered with either “Yes” or “No”, then the subject is included in the SASsol.
- If no question on occurrence of a local or systemic AE is answered with either “Yes” or “No”, then the subject is not included in the SASsol.

It should be noted that the inclusion in the SASsol is defined overall, not by trial vaccine dosing. I.e. if a subject provided information on solicited AEs for the time period after the second CVnCoV/placebo vaccination, but not for the time period after the first CVnCoV/placebo vaccination, the subject is still included in the SASsol.

Table 7: Intensity Grading* for Solicited Systemic Adverse Events

AE	GRADE	DEFINITION
FEVER	0	<38°C
	1	≥38.0 – 38.4°C
	2	≥38.5 – 38.9°C
	3	≥39°C
HEADACHE	0	Absent
	1	Mild, no interference with normal activity
	2	Moderate, some interference with normal activity and/or repeated use of non-narcotic pain reliever >24 hours
	3	Significant; any use of narcotic pain reliever and/or prevents daily activity
FATIGUE	0	Absent
	1	Mild, no interference with normal activity
	2	Moderate, some interference with normal activity
	3	Significant, prevents normal activity
CHILLS	0	Absent
	1	Mild, no interference with normal activity
	2	Moderate, some interference with normal activity
	3	Significant, prevents normal activity
MYALGIA	0	Absent
	1	Mild, no interference with normal activity
	2	Moderate, some interference with normal activity
	3	Significant, prevents normal activity
ARTHRALGIA	0	Absent
	1	Mild, no interference with normal activity
	2	Moderate, some interference with normal activity
	3	Significant, prevents normal activity
NAUSEA/ VOMITING	0	Absent
	1	Mild, no interference with activity and/or 1 – 2 episodes/ 24 hours
	2	Moderate, some interference with activity and/or >2 episodes/ 24 hours
	3	Significant, prevents daily activity, requires outpatient i.v. hydration
DIARRHEA	0	Absent
	1	2 – 3 loose stools over 24 hours
	2	4 – 5 stools over 24 hours

AE	GRADE	DEFINITION
	3	6 or more watery stools or >800 g/24 hours or requires outpatient IV hydration

* FDA TOXICITY GRADING SCALE; I.V. = INTRAVENOUS.

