9.1.2 Primary Safety Endpoints

All safety endpoints are analyzed in all subjects, in subjects seronegative at baseline, and in subjects seropositive at baseline

- Occurrence, intensity and relationship of medically-attended AEs collected to 6 months after the second trial vaccination in all subjects.
- Occurrence, intensity and relationship of SAEs and AESIs collected through EOT Visit in all subjects.
- Occurrence of fatal SAEs through EOT Visit in all subjects.
- Occurrence, intensity and duration of each solicited local AE within 7 days after each trial vaccination in Phase 2b subjects.

- Occurrence, intensity, and duration of each solicited systemic AE within 7 days after each trial vaccination in Phase 2b subjects.
- Occurrence, intensity and relationship of unsolicited AEs occurring within 28 days after each trial vaccination in Phase 2b subjects.
- Occurrence of AEs leading to vaccine withdrawal or trial discontinuation through to EOT Visit in all subjects.

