9.6.1 Safety Analysis Sets (SAS, SAS 2, SASsol)

- The SAS includes all subjects randomized in phase 2b or 3 who received at least one dose of CVnCoV or placebo
- The SASsol includes all phase 2b subjects of the SAS with at least one diary collection indicating the occurrence or lack of occurrence of solicited AEs. See Section 10.5.2 for further details.
- The SAS 2 includes all phase 2b subjects of the SAS

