12.7 Safety Analyses

12.7.1 Adverse Events

Unsolicited AEs, including SAEs, and AESIs and solicited AEs integrated to or recorded on the CRF are coded using MedDRA Version 23.1 or higher, by SOC and PT.

Only TEAEs as defined in Section 10.5.1 are included in AE summaries. In AE listings, all AEs are included.

Solicited AEs occurring on the day of vaccination and the following 7 days are generally included in summaries if not otherwise stated.

Summaries of medically attended AEs only include those AEs that started up to 6 months after the second trial vaccination, see Section 10.5.6 for further details.

Note that for all summaries by SOC and PT, counting is by subject, not event and subjects are only counted once within each SOC and PT. However, if not stated otherwise, all summaries of unsolicited AEs include the number of AEs reported in each category and all events of a subject are then counted.

All AE summary tables are provided overall, by vaccine group, and by age group and vaccine group and are repeated separately in subjects seronegative at baseline and in subjects seropositive at baseline for SARS-CoV-2 N protein antibody levels (see Section 10.6.1).

In general, percentages are based on the number of subjects in the respective analysis set. In summary tables for AEs after the second vaccination, percentages are based on the number of subjects in the respective analysis set who have received the second vaccination.

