12.7.1.2 Analysis of Solicited AEs

The following summaries of solicited AEs within 7 days after each trial vaccination and within 7 days after any trial vaccination are planned:

- Summary of local and systemic AEs, overall and by maximum grade (mild / moderate / severe)
 - Also provided by gender (female/male) for any vaccination, vaccination 1, and vaccination 2.
- Occurrence of local AEs, overall and by maximum grade (mild / moderate / severe)
- Occurrence of systemic AEs, overall and by maximum grade (mild / moderate / severe)
- Occurrence of related systemic AEs, overall and by maximum grade (mild / moderate / severe)
- Duration (days) of local AEs, overall and for grade 3 events
- Duration (days) of systemic AEs, overall and for grade 3 events
- Duration (days) of related systemic AEs, overall and for grade 3 events
- Daily summary of local AEs overall and by maximum grade (mild/moderate/severe) (only for each dose)
- Daily summary of systemic AEs overall and by maximum grade (mild/moderate/severe) (only for each dose)
- Daily summary of related systemic AEs overall and by maximum grade (mild/moderate/severe) (only for each dose)
- Summary of time of onset (Day) overall and for grade 3 solicited AEs, any solicited AEs, local, systemic AEs, and related systemic AEs

- Time of onset (Day) of local AEs, overall and for grade 3 events
- Time of onset (Day) of systemic AEs, overall and for grade 3 events.
- Time of onset (Day) of related systemic AEs, overall and for grade 3 events

All analyses of solicited AEs are provided based on the SASsol.

Before EOT is was decided to not provide any analyses on solicited AEs in the EOT analysis. Therefore some of the above analyses were never performed. For details, please refer to Appendix 6.

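### Per-dose solicited-AE percentages keep subjects with no diary answer for that dose in the denominator, so the primary reactogenicity rates can be biased downward

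*SAP*

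**What the plan says.** - **Endpoint.** SAP 9.1.2 lists among the primary safety endpoints: "Occurrence, intensity and duration of each solicited local AE within 7 days after each trial vaccination in Phase 2b subjects". The systemic endpoint is worded alike.
- **Analysis set.** SAP 9.6.1 defines the SASsol as "all phase 2b subjects of the SAS with at least one diary collection" that shows whether solicited AEs occurred. SAP 10.5.2 makes this concrete: one question answered Yes or No is enough. It adds: "It should be noted that the inclusion in the SASsol is defined overall, not by trial vaccine dosing". Its own example is a subject with information after dose 2 "but not for the time period after the first CVnCoV/placebo vaccination, the subject is still included in the SASsol".
- **Use of the set.** SAP 12.7.1.2: "All analyses of solicited AEs are provided based on the SASsol".
- **Denominators.** SAP 12.7.1: "In general, percentages are based on the number of subjects in the respective analysis set". For tables after dose 2, "percentages are based on the number of subjects in the respective analysis set who have received the second vaccination".
- **Numerator.** SAP 10.5.2 analyses solicited AEs from the CRF unless stated otherwise, and Grade 0 is not entered there as an AE. The investigator may add solicited AEs where the diary looks incomplete.
- **Missing data.** Protocol 10.3.9 sets a valid-case basis and allows imputation only for partial AE and medication dates. The exceptions listed in SAP 10.3 do not cover missing diary answers.

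**The concern.** In the CRF data, a subject who answered No throughout the week after a dose and a subject who never opened the diary that week look the same: neither has a record. The diary data could separate them, but the SAP uses those data only to decide entry to the SASsol, once, for both doses together. The per-dose percentage then treats an unobserved dose period as a period without a reaction. In effect this imputes a favourable value, under a plan that says it does not impute.

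The dose-2 rule shows that a dose-specific denominator was thought necessary. It removes subjects who did not receive dose 2 but keeps recipients who gave no diary answer after it.

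At stake are the occurrence and intensity rates of local and systemic reactions after each dose. Protocol 5.1.1 describes Phase 2b as the main dataset for early conditional approval. If diary completion differs between doses, the comparison of dose 1 with dose 2 is distorted as well.

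**Working it through.** **No stated figure to reproduce.** The documents give no solicited-AE rate, no diary-completion rate and no power calculation for reactogenicity. R, m and f below are assumptions, shown as ranges.

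**Definitions**, for one dose and one arm:
- R: true rate of the reaction.
- m: share of the per-dose denominator with no diary answer for that dose.
- f: share of those subjects' reactions that still reach the CRF.

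**Formula.** Diary responders contribute (1 - m)R to the numerator and non-responders contribute m·f·R. The denominator is 1. So

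reported rate = (1 - m)R + m·f·R = R[1 - m(1 - f)].

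This form assumes that non-responders react at the same rate as responders. The direction does not need that assumption: the shortfall is m(1 - f) times the non-responders' own rate, which cannot be negative.

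**Results for R = 60%:**

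| m | f = 0 | f = 0.5 | f = 1 |
|---|---|---|---|
| 5% | 57.0% | 58.5% | 60.0% |
| 10% | 54.0% | 57.0% | 60.0% |
| 15% | 51.0% | 55.5% | 60.0% |

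In counts: Phase 2b has about 4,000 subjects allocated 1:1, so about 2,000 per arm. At m = 10%, 200 subjects are unobserved after the dose and 200 × 0.60 = 120 reactions are at risk of being lost. At f = 0 the table shows (1,200 - 120)/2,000 = 54%.

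**Other true rates, f = 0.** At m = 2/5/10/20%, a true 50% is reported as 49.0/47.5/45.0/40.0% and a true 80% as 78.4/76.0/72.0/64.0%. At f = 0.5 each shortfall halves.

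**Difference between arms**, for assumed true rates of 80% and 30% (50 points), f = 0:
- m = 10% in both arms: 72 - 27 = 45 points.
- m = 10% active, 5% placebo: 72 - 28.5 = 43.5 points.
- m = 0 active, 10% placebo: 80 - 27 = 53 points.

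The rate in each arm can only fall, but the difference between arms can move either way.

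**Check of a tempting repair.** Suppose the per-dose denominator were diary responders plus any non-responder with an investigator-recorded solicited AE. Non-responders would then enter only as cases. With R = 60% and m = 10%:
- f = 0.5: (0.54 + 0.03)/(0.90 + 0.03) = 61.3%; the SAP rule gives 57.0%.
- f = 1: (0.54 + 0.06)/(0.90 + 0.06) = 62.5%; the SAP rule gives 60.0%, which is exact.

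That repair overshoots, and above about f = 0.7 it is further from 60% than the SAP rule. Restricting both numerator and denominator to responders gives 0.54/0.90 = 60% whatever f is.

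**The case against.** The strongest reply is that a missing diary is not a missing observation. In both Phase 2b groups (Protocol 9.1.1 and 9.1.2), staff ask about solicited AEs at the Day 2 call, the Day 29 visit, the Day 30 call and the Day 43 visit, and what is entered on the CRF counts. Anyone given dose 2 at the Day 29 visit has been asked about dose 1 there. This stands, and it is why f must be in the formula and why the f = 0 column is a worst case. It does not close the gap. Adding events is optional for the investigator, the calls come one day after each dose, and the next visits are four weeks after dose 1 and two weeks after dose 2, so recovery depends on recall.

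The overall definition also follows Protocol 10.2.2, is declared openly, and feeds descriptive tables only (Protocol 10.3.7 plans no formal safety testing). That limits the consequence but does not alter what the percentages mean.

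Finally, SAP 12.7.1.2 plans no solicited-AE analyses at end of trial, and Appendix 6 shows that the daily and time-of-onset tables were never produced. The reach is therefore narrower than every per-dose output. However, Appendix 6 lists the serostatus versions of the per-dose occurrence tables and not the all-subject versions, so the inference is that the main per-dose tables were delivered on this denominator.

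**Conclusion.** The defect holds as a one-directional risk. A subject with no diary answer and no CRF entry for a dose is counted as reaction-free, so per-dose occurrence and intensity rates can be understated and cannot be overstated by this rule. The relative size is m(1 - f): for an assumed R of 60% and m of 5 to 15%, 3 to 9 points at f = 0, half that at f = 0.5, and negligible if diaries are nearly complete. These sizes assume that non-responders react like responders. Rates after any dose carry the same dilution for subjects observed after one dose only. Mean duration and time of onset rest on recorded events and are not diluted.

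A reader might infer more than the documents support:
- That the delivered rates are in fact understated. This needs m above 0 and f below 1, and neither is reported.
- That the loss falls mainly on the CVnCoV arm because saline reactions are rare. No solicited-AE rate is given for either arm and missingness by arm is unknown, so this is an assumption.
- That completion fell after dose 1. Nothing in the documents shows it.

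**What to change.** - For tables after dose 1 and after dose 2, restrict both numerator and denominator to SASsol subjects with at least one answered solicited-AE question after that dose. Do not add a non-responder merely because the investigator recorded a reaction.
- Report, by dose and arm, the number of vaccinated subjects without diary answers, and list the investigator-recorded reactions in those subjects separately.
- Keep the current SASsol tables as supportive, with a footnote that tables after any dose carry the same dilution for subjects observed after one dose only.
- Re-run the main per-dose occurrence tables already delivered.

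The cost is a paragraph in SAP 10.5.2 and 12.7.1, a flag for each dose from diary data already used to define the SASsol, and one re-tabulation. Denominators become slightly smaller and reported rates slightly higher. SAP 6.1 states that version 5.0 was written by an unblinded team, so the new tables must be labelled post hoc. Two limits remain: the result is unbiased only if non-responders react like responders, and one answer still qualifies a subject as observed for the whole week.

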10.5.3 Duration and Time of Onset for Solicited AEs

Duration of solicited local and systemic AEs is defined as the number of **consecutive** days with a recorded local/systemic AE regardless of grade. For example, Fatigue with Grade 1 occurring on day 2 and 3 and day 7 is counted as two separate events with the duration 2 days and 1 day.

The duration of solicited local and systemic AEs ongoing beyond Day 8 after vaccination is defined as

$$\text{Duration} = \text{AE end date} - \text{AE start date} + 1.$$

The AE end date as recorded on the CRF is used in the above formula, except for instances where the recorded date is incomplete in which case the imputed date is used.

The time of onset (Day) of a solicited AE is defined as the day of first occurrence of the AE after the trial vaccination it was assigned to (dose 1 or dose 2, see also Section 10.5.2), regardless of the severity (Grade 1 – Grade 3). The time of onset (Day) of a Grade 3 solicited AE is defined as the first day after the trial vaccination it was assigned to (dose 1 or dose 2, see also Section 10.5.2), on which the AE was first graded as severe (Grade 3), regardless of an earlier occurrence with a lower severity.

Durations are not calculated separately for each grade but rather only for any grade >0 (no matter how often it might transition up and down between grades 1 through 3) or grade=3. Only the longest consecutive duration determined this way is displayed.

Duration and time of onset are calculated separately for events recorded after each trial vaccination.

10.5.4 Unsolicited AEs

Information on unsolicited AEs occurring on each CVnCoV/placebo vaccination day (i.e. dose 1 and 2) and the following 28 days after each CVnCoV/placebo dose are collected for Phase 2b subjects. Data is recorded in the eDiary by the subject to aid AE reporting. The investigator reviews the eDiary and records information on any AEs on the CRF.

Unsolicited AEs are assigned to first or second CVnCoV/placebo dose based on the (reported or imputed) AE date. Unsolicited AEs occurring before dose 2 are assigned to dose 1. Unsolicited AEs occurring after dose 2, are assigned to dose 2. Unsolicited AEs occurring on the day of dose 2 are assigned to either dose 1 or dose 2 as per the following rules:

- If the AE occurred on the day of dose 2 but before vaccination with dose 2, the AE is assigned to dose 1.
- If the AE occurred on the day of dose 2 but on or after vaccination with dose 2, it is assigned to dose 2.
- If the AE occurred on the day of dose 2 and it cannot be determined whether it occurred before, on or after vaccination with dose 2, it is assigned to dose 2.

10.5.5 Adverse Events of Special Interest

The following events are considered and collected as AESIs throughout the trial:

- AEs with a suspected immune-mediated etiology (pIMDs, see Appendix 1)
- Other AEs relevant to SARS-CoV-2 vaccine development or the target disease (see Appendix 2)

AESI are identified as recorded by the investigator in the eCRF. No additional programming is performed to identify (potential) AESIs.

Note: Since it is to be expected that some trial subjects vaccinated with an AV remain in the study, the AESIs collected do not necessarily have to originate from the investigational product but might also have been caused by the AV. For details how this is handled in the analyses please see Section 12.7.1.

10.5.6 Medically Attended AEs

Up to 6 months after second CVnCoV/placebo vaccination (or up to EOT, whatever is earlier), subjects are asked to confirm if they sought medical attention for an AE. Medically attended AEs are defined as AEs with medically-attended visits that are not routine visits for physical examination or vaccination, such as visits for hospitalization, an emergency room visit, or an otherwise unscheduled visit to or from medical personnel (medical doctor) for any reason. The start of a medically attended AE is defined by its start date, irrespective of the date medical attention was sought. A medically attended AE is considered as occurring up to 6 months after second trial vaccination if

$$\text{Start Date of AE} - (\text{Scheduled date of second vaccination} + 1) \leq 180 \text{ days}.$$

i.e. one month is defined as 30 days and the date of the scheduled second vaccination (Day 29) is used in case a subject only received the first vaccination.

Although the 6 months of medically attended AE recording are not re-started when the subject receives an AV, the subject might have received an AV while still being inside the 6 months window after CVnCoV/placebo administration. Thus the medically attended AEs collected might have been caused by an AV. For details how this is handled in the analyses please see Section 12.7.1.

10.5.7 Adverse Events Related to Standardised and Customized MedDRA Queries

Subjects' AEs are filtered with Standardised Medical Dictionary for Regulatory Activities (MedDRA) Queries (SMQs) and Customized MedDRA Queries (CMQs) for the following SMQs/CMQs:

- Anaphylactic reaction (SMQ)
- Convulsions (SMQ)
- Embolic and thrombotic events
- Hypersensitivity (SMQ)
- Immune-mediated/autoimmune disorders (SMQ)
- Liver related investigations, signs and symptoms (Sub-SMQ)
- Paraesthesia, Hypoaesthesia, Hyperesthesia (CMQ)
- Taste and smell disorders (CMQ)

The related terms are listed in Appendix 3.

Although rather unlikely it might happen that study subjects receive an AV during the 28 day post-CVnCoV/placebo injection window where SMQs/CMQs are recorded. Thus the SMQs/CMQs collected do not necessarily have to originate from the investigational product but might also have been caused by an AV or the association of CVnCoV and AV. For details how this is handled in the analyses please see Section 12.7.1.

